3.2 Tamsulosin Hydrochloride (FLOMAX®)

Alpha-blockers are some of the principal treatments for lower urinary tract symptoms due to benign prostatic hyperplasia (BPH). Since some of the symptoms of chronic prostatitis / chronic pelvic pain syndrome are similar to those of BPH, it has been postulated that alpha-blockers may be useful in the treatment of these conditions. Rosette examined the use of the alpha-blocker alfuzosin in men with chronic pelvic pain syndrome(23). In a double blind, placebo-controlled trial, there was no statistically significant difference in reduction in symptoms between men treated with alfuzosin and with placebo. There was, however, a significant difference between treated men and controls in terms of maximal urine flow. Duzendorfer in a similar trial using phenoxybenzamine, however, did find statistically significant improvements in several pain outcomes at six (6) weeks in treated participants compared to controls(24). The treatment group complained of orthostatic changes, which are not unknown in the use of alpha-blockers, but more “uroselective” alpha-blockers now likely reduce these potential side effects. Other studies have also looked at alpha-blockers, principally phenoxybenzamine, and have shown symptomatic improvement in approximately 50% of participants.

Tamsulosin hydrochloride (FLOMAX®) is a newer alpha-adrenergic blocking agent, which has been used extensively for the treatment of BPH. It is a methoxybenzene sulfonamide with a chemical structure that differs from second generation alpha-blockers such as prazosin and alfuzosin, which are quinazoline derivatives. Since it is an alpha 1A selective antagonist, dose titration is not necessary. There is little effect on blood pressure, which improves its overall tolerability. In clinical trials in the treatment of BPH, efficacy as measured by improvement in voiding symptoms and peak flow rates has been reported as significant compared to placebo(25;26). First dose orthostatic effects were rare and there were no significant ECG effects. (See Appendix E).

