4.1.2 Exclusion Criteria

Any participant satisfying any one of the following criteria will **NOT** be eligible to participate in the RCT.

1. Participant has a history of prostate, bladder or urethral cancer.
2. Participant has inflammatory bowel disease (such as Crohn's disease or ulcerative colitis, but not irritable bowel syndrome).
3. Participant has undergone pelvic radiation or systemic chemotherapy.
4. Participant has undergone intravesical chemotherapy.
5. Participant has been treated with intravesical BCG.
6. Participant has been treated for unilateral orchialgia without pelvic symptoms.
7. Participant has an active urethral stricture.
8. Participant has a neurological disease or disorder affecting the bladder.
9. Participant has undergone TURP, TUIP, TUIBN, TUMT, TUNA, balloon dilation of the prostate, open prostatectomy or any other prostate surgery or treatment such as cryotherapy or thermal therapy.
10. Participant has a neurological impairment or psychiatric disorder preventing his understanding of consent and his ability to comply with the protocol.
11. Participant has liver disease.
12. Participant has a known allergy or sensitivity to ciprofloxacin hydrochloride (CIPRO®), tamsulosin hydrochloride (FLOMAX®) or any of their known components.
13. Participant has a history of seizure disorder.
14. Participant is taking theophylline, phenytoin, probenecid or warfarin.
15. Participant requires ongoing use of magnesium, aluminum, or calcium-containing antacids.

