4.1.3 Deferral Criteria

For some conditions, participants may be reconsidered for entry into the trial once the condition has resolved as indicated below.

1. Participant has been treated with tamsulosin hydrochloride (FLOMAX®), doxazosin mesylate (Cardura®), terazosin HCL (Hytrin®), or alpha-blockers in the past four (4) weeks.
2. Participant has been treated with ciprofloxacin hydrochloride (CIPRO®) in the past four (4) weeks.
3. Participant has been treated with antimicrobial agents (oral or parenteral) in the past four (4) weeks.
4. Participant has started, stopped, or changed dose level of **ANY** prostatitis-specific medications within the past four (4) weeks.
5. Participant has had a urinary tract infection, with a urine culture value of >100,000 CFU/ml, within the past three (3) months.

6. Participant has had clinical evidence of urethritis, e.g. including urethral discharge or positive culture, within the past three (3) months, diagnostic of the following sexually transmitted diseases (STDs): gonorrhea, chlamydia, mycoplasma or trichomonas, but not including HIV/AIDS.
7. Participant has had a prostate biopsy in the past three (3) months.
8. Participant has experienced symptoms of acute or chronic epididymitis within the past three (3) months.
9. Participant has begun finasteride (Proscar®) or other androgen hormone inhibitors in the past six (6) months, or stopped finasteride (Proscar®) or other androgen hormone inhibitors within the past six (6) months.
10. Participant has used bioflavonoid agents [Example: Quercetin] in the past two (2) weeks.
11. Participant has been diagnosed with or treated for symptomatic genital herpes in the past twelve (12) months.
12. Participant has been taking zinc or iron supplements within the past two (2) weeks.
13. Participant has been treated with cimetidine in the past two (2) weeks.

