6.3 Concomitant Medications

6.3.1 *Exclusionary Medications*

Participants will be monitored at each clinic and phone visit as to their use of over the counter and prescription medications. During the course of the study, the participant **MAY NOT** initiate or otherwise consume any of the following medications:

1. Tamulosin hydrochloride (FLOMAX®) other than study drug.
2. Ciprofloxacin (CIPRO®) other than study medication.
3. Terazosin HCL (Hytrin®) or doxazosin mesylate (Cardura®).
4. Antimicrobial agents.
5. Finasteride (Proscar®), or other 5-alpha reductase inhibitors, unless taking at baseline. (Note: If the participant is taking one of these medications at baseline, he should continue taking these for the duration of the study.)
6. Warfarin (Coumadin®).
7. Phenytoin (Dilantin®).
8. Probenecid (Benemid®).
9. Antacids.
10. Zinc Supplements.
11. Bioflavonoids (i.e. Quercetin).

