8.4 Potential Adverse Events

8.4.1 *Ciprofloxacin Hydrochloride (CIPRO®)*

During clinical investigation with the tablet, the most frequently reported events, drug related or not, were nausea (5.2%), vomiting (2.0%), abdominal pain/discomfort (1.7%), and rash (1.1%). Most of the adverse events were described as only mild or moderate in severity, abated soon after the drug was discontinued and required no treatment. In randomized, double-blind controlled clinical trials comparing ciprofloxacin tablets (500mg BID) to cefluroxime axetil (250

mg-500 mg BID) and to clarithromycin (500 mg BID) in participants with respiratory tract infections, ciprofloxacin demonstrated a CNS adverse event profile comparable to the control drugs.

In several instances nausea, vomiting, tremor, irritability, or palpitation were judged by the investigator to be related to elevated serum levels of theophylline possibly as a result of the drug interaction with ciprofloxacin. Serious and fatal reactions have been reported in participants receiving concurrent administration of ciprofloxacin and theophylline.

Post-Marketing Adverse Events: Additional adverse events, regardless of the relationship to the drug, reported from worldwide marketing experience with quinolones, including ciprofloxacin, are:

- Change in serum phenytoin
- Postural hypotension, vasculitis
- Agitation, confusion, delirium, dysphasia, myoclonus, nystagmus, toxic psychosis
- Constipation, dyspepsia, flatulence, hepatic necrosis, jaundice, pancreatitis, pseudomembranous colitis
- Aganulocytosis, hemolytic anemia, methemoglobinemia, prolongation of prothrombin time
- Elevation of serum triglycerides, cholesterol, blood glucose, serum potassium
- Myalgia, possible exacerbation of myasthenia gravis, tendinitis/tendon rupture
- Albuminuria, candiduria, renal calculi, vaginal candidiasis
- Anaphylactic reactions, erythema multiforme/Stevens-Johnston syndrome, exfoliative dermatitis, toxic epidermal necrolysis
- Anosmia, taste loss

Adverse Laboratory changes: Changes in laboratory parameters listed as adverse events without regard to drug relationship are listed below:

- Elevated ALT(SGPT), AST(SGOT), alkaline phosphate, LDH, serum bilirubin
- Eosinophilia, leukopenia, decreased blood platelets, elevated blood platelets, pancytopenia
- Elevations of serum creatinine, BUN, crystalluria, cylindruria, hematuria have been reported

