Convulsions, increased intracranial pressure, and toxic psychosis have been reported in patients receiving quinolones, including ciprofloxacin. Ciprofloxacin may also cause central nervous system (CNS) events including: dizziness, confusion, tremors, hallucinations, depression, and, rarely, suicidal thoughts or acts. These reactions may occur following the first dose. If these reactions occur in patients receiving ciprofloxacin, the drug should be discontinued and appropriate measures instituted. As with all quinolones, ciprofloxacin should be used with caution in patients with known or suspected CNS disorders that may predispose to seizures or lower the seizure threshold (e.g. severe cerebral arteriosclerosis, epilepsy), or in the presence of other risk factors that may predispose to seizures or lower the seizure threshold (e.g. certain drug therapy, renal dysfunction). (See **PRECAUTIONS: General, Information for Patients, Drug Interactions** and **ADVERSE REACTIONS**.)

SERIOUS AND FATAL REACTIONS HAVE BEEN REPORTED IN PATIENTS RECEIVING CONCURRENT ADMINISTRATION OF CIPROFLOXACIN AND THEOPHYLLINE. These reactions have included cardiac arrest, seizure, status epilepticus, and respiratory failure. Although similar serious adverse effects have been reported in patients receiving theophylline alone, the possibility that these reactions may be potentiated by ciprofloxacin cannot be eliminated. If concomitant use cannot be avoided serum levels of theophylline should be monitored and dosage adjustments made as appropriate.

Serious and occasionally fatal hypersensitivity (anaphylactic) reactions, some following the first dose, have been reported in patients receiving quinolone therapy. Some reactions were accompanied by cardiovascular collapse, loss of consciousness, tingling, pharyngeal or facial edema dyspnea, urticaria, and itching. Only a few patients had a history of hypersensitivity reactions. Serious anaphylactic reactions require immediate emergency treatment with epinephrine. Oxygen, intravenous steroids, and airway management, including intubation, should be administered as indicated.

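### The list of drugs barred during the study leaves out theophylline and most of the alpha-blocker class, although the entry criteria screen out both

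*Protocol*

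**What the plan says.** Three parts of the protocol bear on this.

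- **Entry.** Exclusion criterion 14 in section 4.1.2 reads "Participant is taking theophylline, phenytoin, probenecid or warfarin". Deferral criterion 1 in section 4.1.3 postpones entry for men treated with tamsulosin, doxazosin, "terazosin HCL (Hytrin®), or alpha-blockers in the past four (4) weeks". The last term makes it a class rule.
- **On study.** Section 6.3.1 says that participants may not "initiate or otherwise consume any of the following medications". Eleven numbered items follow. Warfarin, phenytoin and probenecid are items 6 to 8. The alpha-blockers listed are non-study tamsulosin (item 1) and terazosin and doxazosin (item 3).
- **Stated hazards.** Section 8.4.1 says: "Serious and fatal reactions have been reported in participants receiving concurrent administration of ciprofloxacin and theophylline". The ciprofloxacin label in Appendix D adds: "These reactions have included cardiac arrest, seizure, status epilepticus, and respiratory failure". The tamsulosin label in Appendix E advises against combining it with any other alpha-blocker.

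**The concern.** A man on theophylline cannot enter the trial, but nothing in the list stops a man already in it from starting theophylline while he may be taking ciprofloxacin. The same holds for alpha-blockers other than the three named agents.

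Two things are at stake. The first is safety. Treatment is double-masked, so neither site staff nor an outside prescriber can apply a label warning only to the men on the relevant active drug. The rule has to cover everyone. The second is the tamsulosin comparison. Another alpha-blocker taken in an arm without tamsulosin gives that arm a drug of the class under test and pulls the two groups together. The safety point is much the more important.

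**Working it through.** This is a comparison of provisions, with a little arithmetic on size. The protocol states no figure on this point to reproduce.

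**Step 1. Entry criteria against the on-study list.**

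| Drug or class | At entry | Section 6.3.1 |
|---|---|---|
| Warfarin | Excluded (criterion 14) | Barred (item 6) |
| Phenytoin | Excluded (criterion 14) | Barred (item 7) |
| Probenecid | Excluded (criterion 14) | Barred (item 8) |
| Theophylline | Excluded (criterion 14) | **Absent** |
| Tamsulosin, terazosin, doxazosin | Deferred, 4 weeks | Barred (items 1 and 3) |
| Any other alpha-blocker | Deferred, 4 weeks | **Absent** |
| Zinc | Deferred, 2 weeks | Barred (item 10) |
| Iron | Deferred, 2 weeks | Absent, though section 6.1.1 says to avoid it |
| Cimetidine | Deferred, 2 weeks | Absent |

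Three of the four drugs in criterion 14 carry over; one does not.

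**Step 2. Could item 3 be read as covering the class?** Not naturally. The list uses class terms where it means them, as for antimicrobials, 5-alpha reductase inhibitors and antacids. Item 3 names two agents and stops. Section 3.2 itself mentions three further alpha-blockers. It refers to "second generation alpha-blockers such as prazosin and alfuzosin, which are quinazoline derivatives", and it reports a trial of alfuzosin in chronic pelvic pain syndrome. It also says "Other studies have also looked at alpha-blockers, principally phenoxybenzamine". So 3 of the 6 alpha-blockers named in the protocol body are not barred, and two of those three have been tried in this condition.

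**Step 3. Is there a bar elsewhere?** None was found in the protocol body.

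- Section 5.2 treats theophylline taken with ciprofloxacin as a matter of adjusting the theophylline dose. Read with section 6.3.1, it suggests that the combination is allowed.
- Section 8.6 lets treatment be stopped for concomitant medication judged unacceptable but does not say which drugs those are. Section 6.3.1 is the only list that could.
- Section 6.3.1 promises to monitor medication at every contact, but the schedule in Appendix C places the concomitant medication form only at screening visit 2 and week 6. Diaries and follow-up contacts may still detect use; detecting use does not prohibit it.

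**Step 4. Size.**

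- *Allocation.* There are 46 men per arm and each active drug is given in two of four arms: 2 × 46 = 92, and 92/184 = 50%. A man who starts theophylline therefore has an even chance of being on ciprofloxacin, and a man who starts another alpha-blocker has an even chance of being on tamsulosin. This restates the allocation. It does not estimate how many men would be exposed.
- *Dilution.* Let p be the share of no-tamsulosin men taking another alpha-blocker. Assume that it works as well as tamsulosin and that the tamsulosin arms are unaffected. The expected difference is then 4 × (1 − p). The documents give no value for p, so a range is shown:

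| p | Expected difference (points) | Lost (points) |
|---|---|---|
| 1% | 3.96 | 0.04 |
| 5% | 3.80 | 0.20 |
| 10% | 3.60 | 0.40 |

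One man among the 92 is about 1.1%, or roughly 0.04 points.

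**The case against.** The strongest reply is that the hazard is not hidden and the remaining exposure is small. Theophylline users are excluded and eligibility is confirmed again at screening visit 2. The interaction is described in section 5.2, section 8.4.1 and Appendix D. Medication use is monitored, and treatment can be stopped. What is left is a new start within six weeks by a man not taking the drug at entry. The label does not contraindicate the combination outright; it asks for serum monitoring and dose adjustment if the combination cannot be avoided. The unlisted alpha-blockers appear in section 3.2 only as background, and nothing shows that these men would be prescribed them. The Manual of Procedures and the consent form are not available and may carry fuller instructions.

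Much of this stands as a limit on size. Exposure is probably rare, the dilution is trivial at plausible levels, and it cannot be claimed that sites receive no instruction from any source. Section 5.2 also agrees with the label as a description of risk.

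It does not remove the fault. Every safeguard named either acts at entry or relies on someone recognising a drug as unacceptable without a rule that says so. The label's fallback of serum monitoring is not provided for: Appendix C schedules no theophylline level. Instructions in another document would not correct the protocol's own list.

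**Conclusion.** The concern holds. Section 6.3.1 is an incomplete rule that does not match the entry criteria. The theophylline omission carries the weight, because it involves an interaction that the protocol itself describes as potentially fatal. The alpha-blocker narrowing is a lesser fault, supported by the tamsulosin label and by a possible but small contamination of the tamsulosin comparison.

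The number of men affected cannot be estimated from the documents and is probably low. The efficacy loss is about 0.04 points per 1% of contaminated no-tamsulosin men, assuming equal effect. The planned sample size, power and significance level do not change. The point should be fixed because the correction is nearly free and concerns participant safety.

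**What to change.** In section 6.3.1, add *theophylline* and *any other alpha-blocker*, at least for the six weeks of treatment. Limiting the addition to that period avoids a clash with section 7.7.1, which allows rescue medication after treatment ends.

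Reword the theophylline sentence in section 5.2 to say that the drug is not permitted on study, so that the two sections agree.

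Two consistency lines can go in at the same time. List iron supplements, which section 6.1.1 already says to avoid. Either list cimetidine or state that caution is enough at 0.4 mg; the label's warning is aimed particularly at higher doses.

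The cost is a minor protocol amendment (two list items, two consistency lines and one reworded sentence) and a revised concomitant-medication checklist.

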7 TRIAL TESTS AND PROCEDURES

7.1 Procedural Summary

Prior to the baseline screening, potential participants must have had symptoms of discomfort or pain in the pelvic region for at least a three (3) month period within the last (6) months.

This study is comprised of phases for each participant: i) the *screening phase* and ii) the *treatment and follow-up phase*. The screening phase, which assesses a participant's eligibility via inclusion, exclusion and deferral criteria, will consist of two baseline visits no more than three (3) weeks and no less than seven (7) days apart. Any candidate failing any of the inclusion or exclusion criteria, during either of the screening visits will be considered ineligible for the protocol. Some participants may have their entry into the study deferred to a later time based on the results of the deferral criteria.

7.2 Screening Visit #1

The first screening visit should occur no more than three (3) weeks and no less than one (1) week prior to randomization. During this screening visit, the forms and procedures listed below will be completed. If a participant fails to meet any of the study eligibility criteria, based on the data collected during this visit, he would not be required to complete the physical examination, urinalysis, or urine culture for the purposes of the study. (See **Appendix C**).

1. *Eligibility Criteria.*

Each participant will complete a preliminary screening form that checks whether he meets the initial inclusion/exclusion/deferral criteria. (These criteria will be verified at the second baseline visit.)

2. *Participant Contact Information.*

Participants will be asked to provide the clinical center with their address, phone number, primary care physician, and the name and address of two other contacts. This information will be stored at the CRC and available only to selected study personnel. Participants who have previously enrolled in the CPC will be asked only to update the previous information.

3. *Participant Medical History.*

Each participant will provide the research staff with his general medical history and specific genitourinary medical history. In particular, the participant will be asked to provide information regarding his disease and surgical histories.

4. *Participant Symptom Index.*

[figure not shown]
Each participant will provide the research staff with an assessment of his discomfort/pain by completing the full NIH-CPSI.

5. *Physical Examination.*

Each participant will undergo a focused physical examination. This examination will include an abdominal exam, external genital exam, rectal exam, prostate exam, and perineal exam. Participants enrolled in the CPC who have completed a physical examination within one (1) month of enrolling in the RCT, will not be asked to complete another physical examination.

6. *Urinalysis, Urine and EPS Specimens for Microscopy and Culture.*

Each participant will provide the research staff with three (3) urine specimens and an EPS (expressed prostatic secretion) specimen for analysis and culture. The urine specimen will be collected via the classic “four-glass test” (FGT) described in Meares and Stamey(28). The FGT will be attempted one time only at each of Screening Visit #1 and at the six (6) week clinic visit.

The results from the EPS culture and the post-EPS urine (VB₃), if available, will be compared with the findings from the 1st voided urine (VB₁) and the midstream urine (bladder specimen or (VB₂)). A macroscopic urinalysis will be completed to quantify hemoglobin, protein, and glucose levels, and a microscopic urinalysis will be completed to quantify white blood cells, red blood cells and yeast. All specimens will be cultured for 5

days. The VB₂ culture will also be used to determine UTI status. Although the urinalysis will be performed at the respective CRC, all centers will be required to use the same brand of dipstick. In addition, a portion of the first voided specimen will be tested for chlamydia trachomatis using PCR. (**Appendix F**).

7. Next Visit Preparation.

- i. Appointment scheduling. An appointment will be made for Screening Visit #2, to occur no sooner than one (1) week and no later than three (3) weeks after Screening Visit #1.
- ii. Concomitant medications. Each participant will receive instructions from the RC to bring to Screening Visit #2 all/or a list of all the over-the-counter and prescribed medications that he is currently taking.
- iii. 1-day Voiding Log Supplies and Directions. Each participant will be provided with a voiding log. The participant will be asked to select a typical day, record the date, time and amount of each urination during a complete 24 hour time period. The participant will be asked to return the completed log at Screening Visit #2.

7.3 Screening Visit #2

Participants who still meet all eligibility criteria at this visit will complete the questionnaires and/or undergo the examinations described below, and will continue on to randomization (Section 7.4).

1. *Eligibility Checklist*.

An eligibility checklist confirming that the participant still meets all eligibility criteria will be completed by the RC prior to randomization.

2. *Demographic Questionnaire.*

Each participant will provide the research staff with his demographic information, including date of birth (age), race, marital status, socioeconomic status, level of education.

3. *Concomitant Medications.*

The research staff will record the medications currently being taken by the participant. Participants will be asked to recall their medications if they fail to bring them to the second screening visit.

4. *Participant Symptom/Impact/General Quality of Life Index.*

Each participant will provide the research staff with an assessment of his discomfort/pain by completing the NIH-CPSI. In addition, participants will complete the MOS SF-12, a general Quality of Life Index.

5. *1-day Voiding Log Supplies and Directions.*

A 24-hour voiding log will be collected and reviewed for completion for each participant.

6. *Uroflow and Post Void Residual.*

Participants will undergo urodynamic testing at screening visit #2. The research staff will measure and record participants total voided volume, peak flow, average flow and post-void residual.

7. *Semen Sample Collection.*

A semen sample will be collected and cultured for localized pathogens. Participants are permitted to refuse to provide a semen sample. It is also acceptable if a participant is unable to provide a semen sample. However, participants not providing a semen sample, for whatever reason, must have provided at least one of either an EPS or VB3 sample during screening visit #1.

8. *Medication Diary.*

Participants will be required to maintain a medication diary to record any changes in medication. Participants will also be asked to record all possible adverse events.

